2.1.1 Disposition of Subjects

Subject disposition will be summarized based on all subjects who were screened for the study. The total number of subjects screened and the number (percent) of subjects who failed screening will be summarized, based on data reported on the eligibility assessment in the eCRF.

Confidential Page 19 of 40

The distribution of the number of subjects enrolled by each country/region and site will be summarized for each treatment group and overall.

Study Completion: The number (percent) of randomized (including twins) and treated subjects who completed the treatment period, and 3-month follow-up visits as planned, and those who discontinued from the study (with reasons) will be summarized according to the end of treatment assessment in the eCRF.

A subject data listing of disposition of subjects and the reasons for screen failures will be provided.

2.1.2 Protocol Deviations

Important deviations will be those which are considered to potentially impact upon the interpretation of the primary endpoint in the study. Only important protocol deviations will be listed and tabulated in the CSR.

The following categories of protocol deviations will be reviewed by medical advisors and statisticians prior to unblinding to determine those which are considered important deviations.

- Subjects who do not meet the inclusion criteria
- Subjects who meet any of the exclusion criteria
- Concomitant use of disallowed medications (to be identified through programming)
- Subjects who developed withdrawal criteria during the study but were not withdrawn

Subjects for whom an important protocol deviation was recorded that impacts the interpretation of the overall study efficacy and/or safety outcomes will have a footnote added to applicable output to describe the deviation and its potential impact. Such subjects will be identified as part of the protocol deviation review process, prior to unblinding.

The number and percentage of subjects with important protocol deviations in the FAS will be presented by treatment group.

A listing of these cases will be provided for all important protocol deviations.

2.1.3 Demographics and Baseline Characteristics

Demographic data will be summarized for each treatment group using descriptive statistics on FAS. The following continuous and categorical demographic variables will be summarized and tabulated for each treatment group.

- Gestation age
- Gender
- Country

Confidential Page 20 of 40

- Region (North America, Europe, and Israel)
- Race
- Ethnicity
- Whether on mother's milk

Vital signs (systolic and diastolic blood pressure, pulse rate, respiratory rate and body temperature), birth weight, birth body length and birth head circumference, will be summarized using descriptive statistics for each treatment group.

A subject data listing of demographic and other baseline characteristics at birth will be provided.

2.1.4 Maternal Pregnancy History

The maternal pregnancy history, previous and current, will be summarized for each treatment on FAS according to the maternal pregnancy history assessment in the eCRF.

A subject data listing of maternal pregnancy history will be provided.

2.1.5 Subjects Medical History

The medical history between birth and before the day of first study drug dose will be coded by MedDRA (March 1, 2017 or higher version). The number (percent) of subjects reporting a history of any medical condition, as recorded on the eCRF, will be summarized for each treatment group and overall on FAS.

A subject data listing of medical history will be provided.

2.1.6 Maternal Medication During Pregnancy

All investigator terms for medications recorded on the eCRF will be coded using the World Health Organization (WHO) Drug Dictionary (1 Quarter 2016). The number (percent) of subjects who took medications in the 30 days before the delivery will be summarized for each treatment group on FAS, using the Anatomical Therapeutic Chemical (ATC) Classification and WHO Drug preferred term.

2.1.7 Mother's Chronic Disease

Mother's chronic disease including diabetes, hypoglycemia, hypertension, and other will be summarized as percentage for each treatment group on FAS.

A subject data listing of mother's chronic disease will be provided.

2.1.8 Delivery Outcome

The delivery outcome and type, such as single birth or twin, dizygotic or monozygotic, and delivery route will be summarized as percentage for each treatment group on FAS. APGAR scores will be summarized using descriptive statistics at 1 min, 5 min, and 10 min for each treatment group.

Confidential Page 21 of 40

A subject data listing of delivery outcome will be provided.

2.1.9 Breast Feeding

The volume of mother's milk (ml), total enteral feed, and percentage of mother's milk will be summarized using descriptive statistics by age day for the screening visit.

A subject data listing of breast feeding until treatment initiation will be provided on FAS.

Statistical Analysis Plan V1.3

SAP Date: 06APR2018

2.1.10 Parenteral Nutrition Requirement per Day

Parenteral feeds per day will be summarized using descriptive statistics for each treatment group by day (from screening to discharge) on FAS for the following variables,

- Hours per day
- Volume of PN given per day
- Average number of days of PN per week
- Kcal per day
- Kcals/kg
- Total calories provided by PN per day
- Total volume of "feed" provided by PN per day (Volume of PN/ (volume of PN + volume of EN)

A subject data listing of parenteral feeding per day will be provided.

2.1.11 Total Parenteral Nutrition Intake

Subjects in the following categories will be summarized using descriptive statistics by day for each treatment group,

- Total daily volume (ml)
- Protein/Amino acids (ml)
- Carbohydrates/Dextrose (ml)
- Fat/Lipids (ml)
- Energy (kcal)

2.1.12 Treatment Discharge Assessment

Subjects in the following categories will be summarized using descriptive statistics for each treatment group on Day 28 or discharge day if earlier,

- Discharged to home
- Staying at the primary hospital
- Discharge to a secondary site/hospital

Confidential Page 22 of 40

Statistical Analysis Plan V1.3 SAP Date: 06APR2018

Discharged to a secondary unit within this site/hospital

2.2 EFFICACY ANALYSES

2.2.1 Primary Efficacy Endpoint

2.2.1.1 Primary Analysis

The primary endpoint is the number of days to achieve enteral feeding of at least 150 ml/kg/day for at least 3 consecutive days (NFE). FAS will be used to test the primary efficacy endpoint. See Section 1.4 for explanation of how twins will be handled in this analysis.

For the primary endpoint, the following hypothesis will be tested:

- H₀: The distribution of the number of days to full enteral feeding is the same in the treated and the placebo groups.
- H₁: The distribution of the number of days to full enteral feeding differs in the treated and the placebo groups.

To maintain the overall study-wide two-sided Type I error rate at 0.05, a hierarchically ordered testing procedure, described in section 1.7, will be used.

Testing of the primary endpoint will be by the van Elteren test, stratified by gestational age group and region (North America, Europe, and Israel) with a threshold for statistical significance for each dose of P<0.05.

The average rank will be used for tied NFE values in SAS procedure above. The unique NFE values will retain the ranks as there was no ties.

The Hodges-Lehmann estimator will be used to estimate the treatment differences (each NTRA-2112 dose minus placebo) in days, and their 95% confidence intervals.

Confidential Page 23 of 40

Statistical Analysis Plan V1.3 SAP Date: 06APR2018

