12.4.8. Analyses of Predictor Variables

Effect of covariates: The effect on the primary and key secondary outcomes of the following variables will be assessed:

- GA
- Birth weight

- Gender
- Ethnicity
- Enteral feedings type
 - 1. Own mother's milk only to full enteral feeding
 - 2. Donor breast milk only to full enteral feeding
 - 3. Infant formula only to full enteral feeding
 - 4. Own mother's milk and formula, in any combination of proportions, to full enteral feeding
 - Donor breast milk and formula, in any combination of proportions, to full enteral feeding The methodology will be described in the SAP.

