1.8 EXAMINATION OF SUBGROUPS

Descriptive statistics of effect sizes of treatment on the primary and key secondary endpoints will described in the following subgroups:

Statistical Analysis Plan V1.3

SAP Date: 06APR2018

- Gestation age group
- Region (North America, Europe, and Israel)
- Birth weight (< 750g, $\ge 750g$ and < 1000g, $\ge 1000g$ and < 1500g, $\ge 1500g$)
- Gender
- Ethnicity
- Enteral feedings type:
 - o Only own mother's milk
 - Only donor breast milk
 - Only human milk (combined)
 - o Only Infant formula
 - o Only own mother's milk and formula, in any combination of proportions
 - o Only donor breast milk and formula, in any combination of proportions
 - o Only human milk and infant formula, in any combination of proportions

For an infant to be in one of the above 7 categories, for example "Only own mother's milk", the infant had to be on own mother's milk for enteral feeding every day during the treatment period up to Day 28.

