2.2.1.7 Sensitivity Analysis: Breaking Tied NFE Rankings

For the infants who have the same NFE value which lead to the tied NFE rankings, their baseline enteral feeding volume will be used to break the tie. Specifically, the infant with the lowest baseline enteral feeding volume will be ranked lowest among them, the infant with the second lowest enteral feeding volume will be ranked the second lowest, and so on. For infants who have the same NFE rank and the same baseline enteral feeding volume, their NFE ranks will remain to be tied. For subjects who have unique NFE rankings, they will retain their ranks if there were no ties. For infants who experience NEC (Necrotizing Enterocolitis) and infants who die, their NFE will be assigned to Day 29 and Day 30 without breaking ties by their baseline enteral feeding volume. The individual ranks among subjects experiencing NEC and the individual ranks among subjects who die will be handled according to Section 1.3.3. For subjects who didn't meet the enteral feeding criterion during the treatment period, their NFE will be censored on Day 28 without breaking by their baseline enteral feeding volume. The testing of such NFE ranking will be analyzed in the same way as described in 2.2.1.1 for the van Elteren test, stratified by gestational age group and region (North America, Europe, and Israel).

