2.2.2 Other Secondary Endpoints

The following other secondary endpoints will be analyzed on FAS only.

- Growth velocity (g/kg/day) at 6, 8, and 10 days, the last day of treatment (or Day 28), day of discharge, 3-month follow-up, 12-month follow-up, and 24-month follow up
- Change in Z-score at 6, 8 and 10 days, the last day of treatment (or Day 28), day of discharge, 3-month follow-up, 12-month follow-up, and 24-month follow up from initiation of treatment
- Gain in body weight at 6, 8, and 10 days, the last day of treatment (or Day 28), day of discharge, 3-month follow-up, 12-month follow-up, and 24-month follow up

Confidential Page 27 of 40

• Number and percentage of infants reaching full enteral feeding within 6, 8, and 10 days from initiation of treatment.

- Total number of days receiving parenteral nutrition
- Number of days to 120Kcal/kg/day
- Number of days to wean-off PN

For the continuous variables (growth velocity, z-score, body weight), ANCOVA analysis will be performed at each time point of interest, including treatment, the stratification factors of gestation age and region (North America, Europe, and Israel) as class variables, and the baseline values as a continuous covariate, the estimated treatment differences (NTRA-2112 minus placebo), 95% confidence intervals, and P-values will be provided.

For the variable of number of day to a given event, the van Elteren test stratified for gestation age and region will be performed. The average score will be used for the ties. Infants who experience NEC (Necrotizing Enterocolitis) and infants who die will be assigned the second worst and the worst ranks. The individual ranks among subjects experiencing NEC and the individual ranks among subjects who die will be handled according to Section 1.3.3.

For percent of infants reaching full external feeding, Cochran-Mantel-Haenszel (CMH) test stratified for gestation age and region will be performed.

Statistical testing of these other secondary endpoints will be considered exploratory and will not control for Type I error rate inflation.

No imputation will be performed for the missing values for the other secondary endpoints.

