2.2.4 Analysis of Predictor Variables

The effect of the following predictor variables on the primary and key secondary endpoints will be assessed by calculating descriptive statistics of the primary and key secondary endpoints in each category of predictor class variables on FAS.

- Gestation age group
- Region (North America, Europe, and Israel)
- Birth weight (< 750g, $\ge 750g$ and < 1000g, $\ge 1000g$ and < 1500g, $\ge 1500g$)
- Gender
- Ethnicity
- Enteral feedings type:
 - o Only own mother's milk
 - Only donor breast milk
 - o Only human milk (combined)
 - o Only Infant formula
 - Only own mother's milk and formula, in any combination of proportions
 - Only donor breast milk and formula, in any combination of proportions
 - Only human milk and infant formula, in any combination of proportions

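### The primary and key secondary tests are valid but adjust only for two gestational-age bands and region; adjusting for starting feed volume, birth weight and exact gestational age could add power at little risk

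*SAP*

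**What the plan says.** The confirmatory tests use GA group and region. SAP 2.2.1.1: "Testing of the primary endpoint will be by the van Elteren test, stratified by gestational age group and region", with three regions, so 2 x 3 = 6 strata. SAP 2.2.1.2 has the same strata for the key secondary endpoint (NRD).

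The other values known before treatment appear elsewhere:

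- **Baseline enteral volume.** SAP 2.1.9 summarises "The volume of mother's milk (ml), total enteral feed, and percentage of mother's milk" for the screening visit. Its only efficacy use is in the sensitivity analysis for tied ranks (2.2.1.7), where "their baseline enteral feeding volume will be used to break the tie".
- **Birth weight.** It is a baseline characteristic (2.1.3) and a category in descriptive tables. SAP 1.8 gives "Descriptive statistics of effect sizes of treatment on the primary and key secondary endpoints" by subgroup. In SAP 2.2.4, predictor effects are "assessed by calculating descriptive statistics of the primary and key secondary endpoints in each category of predictor class variables".
- **Gestational age.** It enters as a two-band stratum, as a descriptive category, and as a class covariate alongside region in the twin mixed model (2.2.1.5).

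Protocol 12.4.8 lists GA and birth weight under "Effect of covariates: The effect on the primary and key secondary outcomes of the following variables will be assessed" and leaves the method to the SAP. Protocol 12.4.3 mentions covariates for sensitivity analyses.

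For other endpoints, SAP 2.2.2 says: "For the continuous variables (growth velocity, z-score, body weight), ANCOVA analysis will be performed at each time point of interest", with the baseline value as a covariate. Days-to-event endpoints are handled like the primary: "For the variable of number of day to a given event, the van Elteren test stratified for gestation age and region will be performed".

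**The concern.** The primary endpoint (NFE) counts days until an infant reaches a feeding threshold, so the volume already tolerated at entry is distance already covered. Infants enter between 6 and 120 hours after birth, and at the feeding extremes only those on complete enteral feeding or nil by mouth are excluded, so starting volume can vary. The tie-break in 2.2.1.7 gives the better rank to the infant who started lower, which shows that the sponsor already regards starting volume as relevant. The GA bands span 21 and 22 days, so GA still varies within a band. Protocol Appendix E links complications to both early birth and birth weight.

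If these values predict NFE beyond the strata, leaving them out forgoes power in a test that controls everything after it. Under SAP 1.7, failure of the high-dose primary test ends confirmatory testing. The futility rule in 3.1 also depends on the interim z-value.

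**Working it through.** **1. The plan's own figure.** Inputs from SAP 1.3.3: means 8.0 and 6.6 days, SD 3.5, two-sided 5%, 85% t-test power.

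n = 2(1.960 + 1.036)² x 3.5² / 1.4² = 112.2, so 113 per arm (114 with the exact t-test). The stated 115 is reproduced within 2 infants. The SAP expects at least 80% power from van Elteren. Simulation at 115 per arm gives about 82% when no infant has NEC or dies.

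**2. Formula for the gain.** Let R² be the share of within-stratum variance that the three covariates explain. It is an assumption, because the documents give none. Residual SD = 3.5 x √(1 − R²). Power = Φ(1.4 / (SD√(2/115)) − 1.96).

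| R² | Residual SD | Power, t scale | Starting from 80% | Power if SD is 4.0 |
|---|---|---|---|---|
| 0 | 3.50 | 85.8% | 80.0% | 75.6% |
| 0.1 | 3.32 | 89.2% | 84.0% | 79.9% |
| 0.2 | 3.13 | 92.4% | 87.9% | 84.3% |
| 0.3 | 2.93 | 95.2% | 91.8% | 88.7% |

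SD 4.0 is included because SAP 3.1 itself considers it.

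**3. Simulation of the rank test.** Within each stratum, NFE and each covariate are scored as rank/(n+1) − 0.5. One least-squares slope per covariate is pooled across strata, giving residuals e. The statistic is z = T/√V. T sums, over strata, the treated infants' residuals minus n₁ times the stratum mean of e. V sums n₁n₀/[n(n−1)] x Σ(e − ē)². With no covariates this is van Elteren.

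Settings: 115 per arm, whole-day outcomes, six strata of assumed size, strata with no effect on NFE, R² split equally over the covariates unless stated. There were 8,000 runs per setting (4,000 for f), with a Monte Carlo error of 0.3 to 0.6 point for each power. Entries are adjusted minus van Elteren power, in points.

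| Setting | R²=0 | 0.1 | 0.2 | 0.3 |
|---|---|---|---|---|
| (a) covariates complete | −0.2 | +2.9 | +6.7 | +9.1 |
| (b) 20% of volumes missing at random | −0.5 | +2.7 | +5.6 | +9.0 |
| (c) the lowest 20% of volumes missing | −0.6 | +2.5 | +4.7 | +7.6 |
| (d) all R² in volume, missing as in b | – | +1.9 | +5.2 | +7.3 |
| (d) all R² in volume, missing as in c | – | +0.6 | +2.6 | +3.9 |
| (e) as b, with 5% NEC/death | −0.9 | +2.5 | +4.8 | +8.4 |
| (f) as b, 130 per arm, 11.5% of outcomes imputed | −0.2 | +2.7 | +4.0 | +6.0 |

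In (e) van Elteren power is itself about 74%. A separate simulation with a skewed outcome and 6% worst ranks gave −0.5 / +2.1 / +5.2 / +8.7.

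**4. If the strata are themselves prognostic.** Let GA band explain a share S of the 3.5-day variance. With complete covariates (2,000 runs, each power ±0.9), at R² = 0.1 / 0.2 / 0.3:

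- S = 0.1: +2.8 / +4.8 / +7.7
- S = 0.2: +1.9 / +3.8 / +7.0
- S = 0.3: +2.2 / +3.1 / +5.2

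Van Elteren power is then already about 86, 90 and 93%. With S = 0.2, all R² in volume and the lowest volumes missing, the gain is +0.9 at R² = 0.1 and +1.9 at 0.2. With 5% worst ranks and 20% of volumes missing, the change at R² = 0 / 0.1 / 0.2 / 0.3 is −1 / +3 / +5 / +8 at S = 0 and −1 / +1 / +4 / +7 at S = 0.2.

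**5. Type I error.** Without imputation it is 4.9 to 5.3% adjusted against 4.7 to 5.4% for van Elteren. With imputation it is 4.2 to 4.7% against 4.2 to 5.3%. With worst ranks and missing volumes the adjusted test gives 5.0 to 5.3%.

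**6. Futility.** By normal approximation, take 50 of 130 per arm at the look and the full planned effect. Expected interim z = 0.4√(50/2) = 2.0. Conditional power under the trend falls below 35% when z < 1.03, which has probability Φ(1.03 − 2.0), about 17%. Dividing 2.0 by √(1 − R²) gives about 14, 11 and 9% at R² = 0.1, 0.2 and 0.3.

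**The case against.** The strongest reply is that this is a preference and not a defect. The sample size claims no credit for covariates and still meets its target, and the benefit rests on an R² that nobody has stated. That is correct, and it limits how strongly the point can be put.

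Second, assuming that the strata explain nothing favours adjustment, because van Elteren already captures what they explain. This stands and lowers the range, though a gain remains (step 4). In addition, no setting combines imputation, NEC/death and informatively missing volumes.

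Third, replacing the primary test of a SAP already revised after FDA comments is a large step for an uncertain margin. That is a real cost for the sponsor to weigh.

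Three stronger readings are tempting, and the documents do not support them:

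- *The test is invalid or the trial underpowered.* It is neither: the test holds its size, and simulated power without NEC or death is about 82% against a target of at least 80%.
- *The SAP breaks a protocol commitment to adjust.* Protocol 12.4.8 asks for the effect of covariates on outcomes, not an adjusted treatment test. It leaves the method to the SAP, which takes precedence under Protocol 12.4.
- *Baseline data are ignored, or only in the confirmatory tests.* Volume and GA group have the sensitivity uses noted above, and the SAP's other days-to-event endpoints use the same stratified test.

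**Conclusion.** This is a possible missed efficiency, worth considering, and not an error. In the visible text, three values known before treatment stay out of the confirmatory tests, apart from GA as two bands. For an assumed within-stratum R² of 0.1 / 0.2 / 0.3 the gain is roughly +1 to +3 / +2 to +6 / +4 to +9 points of power. Only the most favourable setting, complete covariates with non-prognostic strata, goes slightly above this (+6.7 at 0.2). Expect the low end if the strata already explain variance, if the lowest volumes are the missing ones, or after imputation. At R² = 0 the loss is at most about 1 point.

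Three limits apply. SAP 2.2.1.1 refers to a SAS procedure that is not in the available text, and the imputation model (2.2.1.3.1) is also absent, so covariate use there cannot be checked. The imputation in setting (f) is therefore an assumed model. All figures are for NFE, because the documents give no design figures for NRD.

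**What to change.** Before unblinding, and preferably before the futility look, amend SAP 2.2.1.1 and 2.2.1.2:

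- Make the confirmatory test a stratified rank analysis of covariance. Keep the GA-group x region strata and the worst ranks for NEC and death.
- Adjust for within-stratum ranks of baseline enteral volume (ml/kg/day), birth weight and GA in days. Give a missing baseline volume the stratum mean rank, assigned blind to arm.
- Use the same statistic within each imputed data set (2.2.1.3), in the tipping-point analysis (2.2.1.4) and for the futility z-value (3.1).
- Keep the unadjusted van Elteren test as a sensitivity analysis and Hodges-Lehmann as the estimate in days.

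**Cost.** No new data or enrolment. The price is a documented amendment with matching code, a less familiar test, an estimate in days that does not match the test exactly, and up to about 1 point of power if the covariates are not prognostic.

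**Fallback.** If the sponsor will not change the primary test, add a rank-ANCOVA sensitivity analysis or put these covariates in the 2.2.1.5 mixed model. That costs less and fits Protocol 12.4.3, but does not raise confirmatory power.

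**Separate point.** SAP 1.6.1 makes the randomization day Day 1, while 1.6.2 makes it the day of first dose. These should be reconciled so that baseline volume is unambiguous.
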